#### **4.2.2.4** Restrictions regarding gamete donation

Gamete donation must not be performed from the time of the first dose of the investigational drug, and for at least 3 months after the last dose of the investigational drug.

### **4.3 TREATMENT COMPLIANCE**

Compliance will be assured by administration of all trial medication in the study centre. This is performed by a qualified physician. In the MD part the unmasked injector with no other involvement in the trial will administer the trial medication.

Patients who are non-compliant (for instance, who do not appear for scheduled visits or violate trial restrictions) may be removed from the trial and the CRF will be completed accordingly (for further procedures, please see Section [3.3.4.1](#)).

## 5. ASSESSMENTS

### 5.1 ASSESSMENT OF EFFICACY

For the endpoints, baseline is defined as the value at Visit 2; if not measured at Visit 2 then baseline is the value at Visit 1. All ophthalmologic examinations will be performed on both eyes, as described below.

Centrally collected ophthalmological data (color fundus photography, SD-OCT, OCT-A) will be transferred from the Central Reading Center (CRC) to the sponsor's database. The local measurement data (BCVA, Slit lamp, IOP, LLBCVA) will be transferred to the appropriate eCRFs and will remain at the study sites as source documents.

If clinically significant worsening is observed in the assessments of efficacy during the study, it will be reported as AE in the eCRF (please also refer to Section [5.2.7](#)).

#### SD-OCT/OCT-Angiography

The retinal layers and their thickness can be visualized and measured by SD-OCT. The assessment will be performed by a qualified person, and only specified OCT equipment will be used. OCT-A is a non-invasive imaging technique that provides high-resolution volumetric blood flow information without the use of dye. The assessment is also performed by a qualified person, and only specified device(s) will be used.

OCT images will be sent to an independent CRC for evaluation. A detailed manual for OCT image acquisition and data transmission will be provided.

#### Visual Acuity measured by ETDRS letter charts

BCVA will be measured using the early treatment diabetic retinopathy study (ETDRS) VA chart starting at a test distance of 4 meters. The BCVA score is the number of letters read correctly by the patient. The assessment will be performed by a trained person under specified conditions regarding examination room and equipment.

[REDACTED]

[REDACTED]

## 5.2 ASSESSMENT OF SAFETY

### 5.2.1 Dose limiting event

A DLE is defined as the occurrence of any of the following events in the study eye within the evaluation period (7 days after drug administration):

- Development of sterile endophthalmitis and/or sterile inflammation of the vitreous of grade 3+ according to the NEI Grading of vitreous haze, and anterior chamber cells of 3+ according to the Standardization of Uveitis Nomenclature (SUN) working group (WG) grading scheme (see Table 5.2.1: 1 below) and a duration of 5 or more days between day 1 and day 8
- Visual loss of more than 15 letters at any given time-point
- Persistent IOP over 30 mmHg for 3 days
- Signs of vascular occlusion in a 1st (the main branch) or 2nd degree (the vessel after the first bifurcation of the main branch) retinal vessel, including peripheral retinal hemorrhages in the area supplied by the occluded vessel (hemorrhage of the macula would not be included as this is a symptom of the disease).

Table 5.2.1: 1 The SUN Working Group Grading Scheme for Anterior Chamber Cells ([R18-1136](#))

Grade	Cells in Field 
0	<0
0.5+	1-5
1+	6-15
2+	16-25
3+	26-50
4+	>50

 Field size is a 1 mm by 1 mm slit beam.

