## CLINICAL TRIAL PROTOCOL SYNOPSIS

Company name	Boehringer Ingelheim
Protocol date	16 Jan 2020
Revision date	07 Oct 2022
BI trial number	1436-0001
Title of trial	A First-in Human trial to study safety and tolerability of single rising intravitreal dOses (open label, non-randomized, uncontrolled) and in addition the early biological response of multiple intravitReal dosing (single-masked, raNdomized, sham-controlled) of BI 764524 in panretinaL photocoagulation (PRP) treated proLiferative diabetic retinopathy (PDR) patients with diabetic macular ischemia (DMI) – the HORNBILL Study
Co-ordinating Investigator	 Phone:  Fax: 
Trial sites	Multi-centre trial
Clinical phase	I/IIa
Trial rationale	
Diabetic macular ischemia (DMI) is a chronic complication of diabetic retinopathy (DR), and can potentially lead to visual functional loss. Currently, there are no approved or effective treatments to prevent either onset or progression of DMI in laser-treated PDR patients.
 
As a transition from preclinical investigations to clinical development in this first-in human trial, the maximum feasible dose (MFD) of BI 764524 will be determined and safety, tolerability and early biological response will be investigated in DMI volunteer patients.
 
This trial will include patients affected by DMI with significant visual loss since intravitreal (IVT) injections in patients without the condition would not be considered ethically justifiable.

Trial objectives	The objective of this trial is to determine the maximum feasible dose (MFD) for further development of BI 764524 in patients with pan-retinal coagulation treated proliferative diabetic retinopathy (PDR) patients with diabetic macular ischemia (DMI) based on the primary endpoint occurrence of dose limiting events (DLE) during MFD evaluation period of 7 days (single rising dose (SRD)) or 28 days after last administration (multiple dosing (MD)) and to investigate the safety, tolerability and early biological response after IVT injections of BI 764524.
-------------------------	--

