## 2. TRIAL OBJECTIVES AND ENDPOINTS

### 2.1 MAIN OBJECTIVES, PRIMARY AND SECONDARY ENDPOINTS

#### 2.1.1 Main objectives

The objective of this trial is to determine the maximum feasible dose (MFD) for further development of BI 764524 in patients with pan retinal coagulation treated proliferative diabetic retinopathy (PDR) patients with diabetic macular ischemia(DMI) based on the primary endpoint occurrence of dose limiting events (DLE) during MFD evaluation period of 7 days (SRD) or 28 days after last administration (MD) and to investigate the safety, tolerability and early biological response after multiple IVT injections of BI 764524.

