#### 5.2.7.1.4 Adverse events of special interest

The term adverse events of special interest (AESI) relates to any specific AE that has been identified at the project level as being of particular concern for prospective safety monitoring and safety assessment within this trial, e.g. the potential for AEs based on knowledge from other compounds in the same class. AESIs need to be reported to the sponsor’s Pharmacovigilance Department within the same timeframe that applies to SAEs, please see Section [5.2.7.2.2](#).

The following are considered as AESIs:

- Hepatic injury  
A hepatic injury is defined by the following alterations of hepatic laboratory parameters:
  - o An elevation of AST (aspartate transaminase) and/or ALT (alanine transaminase)  $\geq 3$ -fold ULN combined with an elevation of total bilirubin  $\geq 2$ -fold ULN measured in the same blood sample, or
  - o Aminotransferase (ALT, and/or AST) elevations  $\geq 10$ -fold ULN

These lab findings constitute a hepatic injury alert and the patients showing these lab abnormalities need to be followed up according to the ‘DILI checklist’ provided in the eDC.

In case of clinical symptoms of hepatic injury (icterus, unexplained encephalopathy, unexplained coagulopathy, right upper quadrant abdominal pain, etc.) without lab results (ALT, AST, total bilirubin) available, the Investigator should make sure that these parameters are analysed, if necessary in an unscheduled blood test. Should the results meet the criteria of hepatic injury alert, the procedures described in the DILI checklist should be followed.

All AEs meeting the criteria for a dose limiting event (DLE) as defined in Section [5.2.1](#) are defined as AESIs for this trial.

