6. GENERAL ANALYSIS DEFINITIONS

6.1 TREATMENT(S)

For basic study information on treatments to be administered, assignment of treatment groups, selection of doses, refer to CTP Sections 3 and 4.

The trial will consist of an SRD part followed by an MD part. The SRD part will be conducted open-label, non-randomized, and uncontrolled, whereas the MD part will be single-masked, randomized and sham-controlled.

It was planned to assign up to 45 patients in total, up to 15 in the SRD part in (3 sequential dose groups comprising at least 3 patients each) and 30 in the MD part (20 patients on BI 764524 and 10 patients on sham injection).

With recruitment completed, the actual numbers enrolled are 12 patients in the SRD part and 32 in the MRD part (3 patients discontinued and were replaced).

For details of dosage and formulation see [Tables 6.1:1](#) and [6.1:2](#) below.

Table 6.1: 1 Treatments and labels used in the analysis – SRD part

Dose group	Treatment	Description	Short label
1	D	BI 764524 █████ SRD	BI █████ SRD
2	E	BI 764524 █████ SRD	BI █████ SRD
3	F	BI 764524 █████ SRD	BI █████ SRD

Table 6.1: 2 Treatments and labels used in the analysis – MD part

Dose group	Treatment	Descriptive	Short label
1	A	BI 764524 █████g	BI █████ MD
2	S	Sham injection	Sham MD

Section 7.3.4 of the CTP:

For BI 764524 the residual effect period (REP) after IVT administration is not known. Therefore, all AEs with an onset between start of treatment and the respective EOS visit will be assigned to the on-treatment period for evaluation.

The following separate study phases will be defined for the analyses of AEs:

- **Screening** (ranging from 0:00h (midnight) on the day of informed consent until the first administration time of BI 764524)
- **On treatment**
 - **BI treatment** (separately for each treatment, ranging from the time of first administration of BI 764524 until 0:00h (midnight) on the day after trial completion date)

The following AE displays will be provided in the report:

Section 15.3 (presented separately for SRD and MD part) and Appendix 16.1.13.1.8 (for ClinicalTrials.gov and EudraCT) of the CTR displays:

In these displays, the -on- treatment phase will be analysed (labelled with the short label of the study treatment). Screening will not be included in this analysis.

The following totals will be provided in section 16.1.13.1.8 in addition:

- a total over all on-treatment phases ("Total")

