7.8.1 Adverse Events

AEs will be coded with the most recent version of MedDRA.

The analyses of AEs will be descriptive in nature and will be based on BI standards as presented in “Analysis and Presentation of Adverse Event Data from Clinical Trials – Display Template” [BI-KMED-BDS-HTG-0041] ([9](#)).

Unless otherwise specified, the analyses of AEs will be descriptive in nature. All analyses of AEs will be based on the number of subjects with AEs and NOT on the number of AEs.

For analysis multiple AE occurrence data on the eCRF will be collapsed into an AE provided that all of the following applies:

- All AE attributes are identical (lower level term (LLT), intensity, action taken, therapy required, seriousness, reason for seriousness, relationship, outcome, AE of special interest (AESI))
- The occurrences were time-overlapping or time-adjacent (time-adjacency of two occurrences is given if the second occurrence started within one hour after end of the first occurrence)

Section 5.2.7.1.4 of the CTP: *The following are considered as AESIs:*

- *Hepatic injury*
A hepatic injury is defined by the following alterations of hepatic laboratory parameters:
 - *An elevation of AST (aspartate transaminase) and/or ALT (alanine transaminase) ≥ 3 -fold ULN combined with an elevation of total bilirubin ≥ 2 -fold ULN measured in the same blood sample, or*
 - *Aminotransferase (ALT, and/or AST) elevations ≥ 10 fold ULN*

These lab findings constitute a hepatic injury alert and the patients showing these lab abnormalities need to be followed up according to the 'DILI checklist' provided in the eDC. In case of clinical symptoms of hepatic injury (icterus, unexplained encephalopathy, unexplained coagulopathy, right upper quadrant abdominal pain, etc.) without lab results (ALT, AST, total bilirubin) available, the Investigator should make sure that these parameters are analysed, if necessary in an unscheduled blood test. Should the results meet the criteria of hepatic injury alert, the procedures described in the DILI checklist should be followed. All AEs meeting the criteria for a dose limiting event (DLE) as defined in Section 5.2.1 are defined as AESIs for this trial.

The analysis of adverse events will be based on the concept of treatment emergent adverse events.

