Section 5.2.7.1.4 of the CTP: *For BI 764524 the residual effect period (REP) after IVT administration is not known. Therefore, all AEs with an onset between start of treatment and the respective EOS visit will be assigned to the on-treatment period for evaluation.*

According to ICH E3 (11), AEs classified as 'other significant' needs to be reported and will include those non-serious and non-significant adverse events with

- (i) 'action taken = discontinuation' or 'action taken = reduced', or
- (ii) marked haematological and other lab abnormalities or lead to significant concomitant therapy as identified by the Clinical Monitor/Investigator at the RPM/DBLM at the latest.

An overall summary of AEs (including number of patients with any AE, DLEs, drug related AEs, ocular AEs, AESIs, serious AEs and drug related serious AEs) will be presented.

The frequency of patients with AEs will be summarized by treatment, primary system organ class (SOC) and preferred term (PT). Separate tables will be provided for patients with other significant AEs according to ICH E3 (11), for patients with serious AEs, for patients with drug-related AEs, for patients with drug related serious adverse events for patients with AESIs, for patients with ocular AEs, and for patients with ocular AEs in the study eye.

The SOC and PTs will be sorted by frequency (within SOC). The MedDRA version number will be displayed as a footnote in the respective output.

In addition, frequencies of patients with non-serious AEs that had an incidence of > 5% for at least one treatment will be summarised by treatment, primary SOC and PT.

For disclosure of adverse events on EudraCT additional information not included in a standard AE analysis will be performed. The following three entries will be created:

- Adverse Events per arm for disclosure on EudraCT
- Non-serious Adverse Events for disclosure on EudraCT
- Serious Adverse Events for disclosure on EudraCT

For all ocular adverse events, ocular symptoms will be listed in addition.

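### The only DLE definition runs 7 days from dosing, but the plan also applies it to the MD part, where the stated period is 28 days after the last administration

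*Protocol*

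**What the plan says.** Protocol 5.2.1 gives one DLE definition with four criteria, all judged "in the study eye within the evaluation period (7 days after drug administration"). The inflammation criterion is further tied to the calendar: "and a duration of 5 or more days between day 1 and day 8". There is no MD version.

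The objective in Protocol 2.1.1 is based on "dose limiting events (DLE) during MFD evaluation period of 7 days (SRD) or 28 days after last administration (MD"), and the synopsis agrees: "during MFD evaluation period of 7 days (single rising dose (SRD)) or 28 days after last administration (multiple dosing (MD")).

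The definition is used beyond the SRD part in these places:

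- Protocol 7.1 names DLEs and drug-related adverse events as the basis for assessing the main objectives, and says that these will be compared descriptively between the MD treatment groups.
- Protocol 5.2.7.1.4 makes any adverse event meeting the 5.2.1 criteria an AESI, to be reported to the sponsor's "Pharmacovigilance Department within the same timeframe that applies to SAEs".
- SAP 7.8.1 repeats the rule: "All AEs meeting the criteria for a dose limiting event (DLE) as defined in Section 5.2.1 are defined as AESIs for this trial". Its overall summary includes "number of patients with any AE, DLEs, drug related AEs, ocular AEs, AESIs, serious AEs and drug related serious AEs".
- SAP 6.1 places the report's adverse event displays in "Section 15.3 (presented separately for SRD and MD part").

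**The concern.** The period in the definition and the period in the objective differ, and nothing in the SAP says which one governs the MD part. The 7-day window suits the SRD schedule, which has eye examinations on days 4 and 8. The MD schedule has no counterpart.

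Three things are at stake:

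- the meaning of any MD DLE count and of the DLE-derived part of the MD AESI count;
- the comparison between active and sham that Protocol 7.1 announces;
- 24-hour reporting of a non-serious event that meets the clinical criteria but starts more than 7 days after an injection.

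Intraocular inflammation is a listed product risk (Protocol 1.4.2), and the MD part is the first repeat dosing in humans.

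**Working it through.** The plan gives no figure to reproduce. The check is day arithmetic on Flow Chart II.

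**Inputs.** Permitted visit days are:

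- Visit 2: day 1
- Visit 3: 29 ± 3 = 26–32
- Visit 4: 57 ± 3 = 54–60
- Visit 5: 85 ± 7 = 78–92

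Injections are given at Visits 2, 3 and 4, after that visit's eye assessments (Protocol 6.2.2), so the first scheduled eye examination after an injection is at the next visit.

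**Gap from injection to next scheduled eye examination**

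| Injection | Shortest | Longest |
|---|---|---|
| 1 | 26 − 1 = 25 days | 32 − 1 = 31 days |
| 2 | 54 − 32 = 22 days | 60 − 26 = 34 days |
| 3 | 78 − 60 = 18 days | 92 − 54 = 38 days |

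The minimum is 18 days. None of the 30 × 3 = 90 planned MD injections (20 × 3 = 60 active, 30 sham) has a scheduled examination within 7 days. Inside the 7-day window, information can come only from post-dose monitoring of at least 1 hour (Protocol 4.1.5), an unscheduled visit (6.2.3) or a recorded onset date (8.3.1).

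**Coverage of the stated MD period.** Protocol 2.1.1 can be read in two ways.

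*From first injection to 28 days after the last.* Length = (57 + 28) − 1 = 84 planned days (81 to 87 with the Visit 4 window).

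- Seven days after each injection: 3 × 7 = 21; 21/84 = 25%.
- Inflammation clause read as study days 1 to 8: 7/84 = 8.3%. This excludes injections 2 and 3, which are 40 of the 60 planned active injections.

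*Only the 28 days after the last injection.*

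- Seven days after injection 3: 7/28 = 25%.
- Study days 1 to 8: 0/28.

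**Can Visit 5 stand in for day 28 after injection 3?** There are 7 × 15 = 105 permitted pairs of Visit 4 and Visit 5 days. Visit 5 is at most 28 days after Visit 4 in 5 + 6 + 7 + 8 + 9 + 10 + 11 = 56 of them (53%). This counts calendar combinations and is not a probability. It shows only that the window must close on onset date and not at Visit 5.

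**The case against.** The strongest reply is that DLEs are an SRD concept. Wherever they drive a decision, the part is SRD: the SRD primary endpoint, the Bayesian escalation model, patient replacement, and SAP 7.4.1, which quotes 5.2.1 under the SRD heading. The MD primary endpoint is drug-related adverse events to end of study, which already runs past 28 days after the last dose. On this view the 28-day phrase is what should go. That would be coherent, but current text stands against it: Protocol 2.1.1 and the synopsis name an MD period, 7.1 announces an MD comparison, and the AESI rule is not limited to SRD. Deleting the phrase would also withdraw part of the stated objective after recruitment.

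A reader might infer that the SAP expressly plans a DLE row for the MD part. It does not. That row follows from the unrestricted summary list in SAP 7.8.1 read with the split of displays in SAP 6.1. Protocol 7.1 is the more direct evidence.

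A reader might also infer that late inflammation in the MD part would go unnoticed. The documents do not support that. Such events remain in the ocular adverse event tables and the severity tabulation, and in the MD primary endpoint if judged drug-related. The important-medical-event criterion (Protocol 5.2.7.1.2), the sponsor's always-serious list (5.2.7.1.3), the stopping rule (3.3.4.3) and regular safety committee review (3.1, 8.7) do not depend on DLE status. Because the always-serious list is not reproduced, the number of DLE-type events that would stay non-serious is unknown.

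Finally, a longer window does not improve detection. Events that resolve between four-weekly examinations can be missed under either window, and intra-ocular pressure above 30 mmHg for 3 days cannot be shown by four-weekly readings. That part of the objection stands and limits what the fix can claim.

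**Conclusion.** The inconsistency is real and is in the current text. An MD DLE count, or the DLE-derived part of the MD AESI count, made under 5.2.1 does not address the period in the objective. It covers 25% of that period if applied per injection. The lower figures (8.3%, or none) apply only to inflammation and only if the day 1 to day 8 clause is read as study days. All figures use the planned schedule and its permitted windows. The plan gives no event rate, so the number of patients affected cannot be estimated.

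The consequence is limited to the DLE/AESI label, expedited reporting of non-serious cases, and the reading of the MD counts. The SRD primary endpoint, dose escalation and MD primary endpoint are untouched. A zero in an MD DLE display should not be read as absence of such events over the 28-day period, and even with a corrected window it would not exclude transient ones.

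**What to change.** In SAP 7.8.1, and in Protocol 5.2.1 and 5.2.7.1.4 if the protocol is amended again, state for the MD part:

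- The DLE/AESI window is onset from first injection (active or sham) to 28 days after the last injection given.
- The day 1 to day 8 limit does not apply. The 5-day inflammation duration is judged from the recorded course at grade 3+ where available, and otherwise from adverse event dates and flagged as such, because event duration is not the same as time at that grade.
- Grades, letter and pressure thresholds and the SRD definition stay unchanged.

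Label the MD counts as using a window specified after recruitment: SAP 6.1 reports recruitment complete, and Protocol 4.1.6.1 has sponsor data handled open label. List each case with days from the preceding injection to onset, so that the 7-day count can be read off. Add a note that examinations are about four weeks apart and a zero does not exclude transient events.

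The cost is a few sentences, a table label and a re-tabulation, with no new visit. Onset dates are mandatory and end dates are collected where available (Protocol 8.3.1), and adverse event analysis is not visit-based (SAP 6.7). Inflammation grades may have to be taken from source documents for affected patients. A longer window will also collect more background events, such as visual loss from vitreous haemorrhage; the sham arm shows that background. The change cannot restore 24-hour reporting for past events.

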### 5.2.2 Physical examination

A complete physical examination will be performed at the time points specified in the [Flow Chart I](#) and [Flow Chart II](#). It includes at a minimum general appearance, neck, lungs, cardiovascular system, abdomen, extremities, skin and measurement of height and body weight.

The results must be included in the source documents available at the site.

